3.3 Inclusion of Women and Minorities

The target population is all adults aged 14 or greater with MLL (KMT2A) rearranged AML (subject to additional inclusion and exclusion criteria for reasons of medical safety). We will make every effort to enroll women and minority patients.

NIH policy requires that women and members of minority groups and their subpopulations be included in all NIH-supported biomedical and behavioral research projects involving NIH-defined clinical research unless a clear and compelling rationale and justification establishes to the satisfaction of the funding Institute & Center (IC) Director that inclusion is inappropriate with respect to the health of the subjects or the purpose of the research. Exclusion under other circumstances must be designated by the Director, NIH, upon the recommendation of an IC Director based on a compelling rationale and justification. Cost is not an acceptable reason for exclusion except when the study would duplicate data from other sources. Women of childbearing potential should not be routinely excluded from participation in clinical research. Please see <http://grants.nih.gov/grants/funding/phs398/phs398.pdf>.

Planned enrollment targets are provided in tables in section 9.2.

4. REGISTRATION PROCEDURES

4.1 Investigator and Research Associate Registration with CTEP

Food and Drug Administration (FDA) regulations require IND sponsors to select qualified

investigators. NCI policy requires all persons participating in any NCI-sponsored clinical trial to register and renew their registration annually. To register, all individuals must obtain a CTEP Identity and Access Management (IAM) account (<https://ctepcore.nci.nih.gov/iam>). In addition, persons with a registration type of Investigator (IVR), Non-Physician Investigator (NPIVR), or Associate Plus (AP) (i.e., clinical site staff requiring write access to OPEN or RAVE or acting as a primary site contact) must complete their annual registration using CTEP’s web-based Registration and Credential Repository (RCR) (<https://ctepcore.nci.nih.gov/rcr>). Documentation requirements per registration type are outlined in the table below.

| Documentation Required | IVR | NPIVR | AP | A |
|---|-----|-------|----|---|
| FDA Form 1572 | ✓ | ✓ | | |
| Financial Disclosure Form | ✓ | ✓ | ✓ | |
| NCI Biosketch (education, training, employment, license, and certification) | ✓ | ✓ | ✓ | |
| HSP/GCP training | ✓ | ✓ | ✓ | |
| Agent Shipment Form (if applicable) | ✓ | | | |
| CV (optional) | ✓ | ✓ | ✓ | |

An active CTEP-IAM user account and appropriate RCR registration is required to access all CTEP and CTSU (Cancer Trials Support Unit) websites and applications. In addition, IVRs and NPIVRs must list all clinical practice sites and IRBs covering their practice sites on the FDA Form 1572 in RCR to allow the following:

- Added to a site roster
- Assigned the treating, credit, consenting, or drug shipment (IVR only) tasks in OPEN
- Act as the site-protocol PI on the IRB approval

Additional information can be found on the CTEP website at <https://ctep.cancer.gov/investigatorResources/default.htm>. For questions, please contact the RCR **Help Desk** by email at [contact].

4.2 Site Registration

This study is supported by the NCI Cancer Trials Support Unit (CTSU).

Each investigator or group of investigators at a clinical site must obtain IRB approval for this

protocol and submit IRB approval and supporting documentation to the CTSU Regulatory Office before they can be approved to enroll patients. Assignment of site registration status in the CTSU Regulatory Support System (RSS) uses extensive data to make a determination of whether a site has fulfilled all regulatory criteria including but not limited to the following:

- An active Federal Wide Assurance (FWA) number
- An active roster affiliation with the Lead Network or a participating organization
- A valid IRB approval
- Compliance with all protocol specific requirements.

In addition, the site-protocol Principal Investigator (PI) must meet the following criteria:

- Active registration status
- The IRB number of the site IRB of record listed on their Form FDA 1572
- An active status on a participating roster at the registering site

Sites participating on the NCI CIRB initiative that are approved by the CIRB for this study are not required to submit IRB approval documentation to the CTSU Regulatory Office. For sites using the CIRB, IRB approval information is received from the CIRB and applied to the RSS in an automated process. Signatory Institutions must submit a Study Specific Worksheet for Local Context (SSW) to the CIRB via IRB Manager to indicate their intent to open the study locally. The CIRB's approval of the SSW is then communicated to the CTSU Regulatory Office. In order for the SSW approval to be processed, the Signatory Institution must inform the CTSU which CIRB-approved institutions aligned with the Signatory Institution are participating in the study.

4.2.1 Downloading Regulatory Documents

Site registration forms may be downloaded from the NCI#10212 protocol page located on the CTSU Web site. Permission to view and download this protocol is restricted and is based on person and site roster data housed in the CTSU RSS. To participate, Investigators and Associates must be associated with the Corresponding or Participating protocol organization in the RSS.

- Go to <https://www.ctsuo.org> and log in using your CTEP-IAM username and password.
- Click on the Protocols tab in the upper left of your screen.
- Either enter the protocol # in the search field at the top of the protocol tree, or
- Click on the By Lead Organization folder to expand, then select LAO-OH007, and protocol #10212.
- Click on LPO Documents, select the Site Registration documents link, and download and complete the forms provided. (Note: For sites under the CIRB initiative, IRB data will load to RSS as described above.)

4.2.2 Requirements For NCI #10212 Site Registration

- IRB approval (For sites not participating via the NCI CIRB; local IRB)

documentation, an IRB-signed CTSU IRB Certification Form, Protocol of Human Subjects Assurance Identification/IRB Certification/Declaration of Exemption Form, or combination is accepted)

4.2.4 Checking **Site** Registration Status

You can verify your site registration status on the members' section of the CTSU website.

- Go to <https://www.ctsu.org> and log in to the members' area using your CTEP-IAM username and password
- Click on the Regulatory tab at the top of your screen
- Click on the Site Registration tab
- Enter your 5-character CTEP Institution Code and click on Go

Note: The status given only reflects compliance with IRB documentation and institutional compliance with protocol-specific requirements as outlined by the Lead Network. It does not reflect compliance with protocol requirements for individuals participating on the protocol or the enrolling investigator's status with the NCI or their affiliated networks.

4.3 Patient Registration

4.3.1 OPEN / IWRS

Patient enrollment will be facilitated using the Oncology Patient Enrollment Network (OPEN). OPEN is a web-based registration system available to users on a 24/7 basis. It is integrated with the CTSU Enterprise System for regulatory and roster data interchange and with the Theradex Interactive Web Response System (IWRS) for retrieval of patient registration/randomization assignment. Patient enrollment data entered by Registrars in OPEN / IWRS will automatically transfer to the NCI's clinical data management system, Medidata Rave.

The OPEN system will provide the site with a printable confirmation of registration and treatment information. Please print this confirmation for your records.

4.3.2 OPEN/IWRS User Requirements

OPEN/IWRS users must meet the following requirements:

- Have a valid CTEP-IAM account (*i.e.*, CTEP username and password).
- To enroll patients or request slot reservations: Be on an ETCTN Corresponding or Participating Organization roster with the role of Registrar. Registrars must hold a minimum of an AP registration type.
- To approve slot reservations or access cohort management: Be identified to Theradex as the "Client Admin" for the study.
- Have regulatory approval for the conduct of the study at their site.

Prior to accessing OPEN/IWRS, site staff should verify the following:

- All eligibility criteria have been met within the protocol stated timeframes.
- If applicable, all patients have signed an appropriate consent form and Health Insurance Portability and Accountability Act (HIPAA) authorization form.

4.3.3 Patient Enrollment Instructions

For trials with slot reservation requirements, OPEN will connect to IWRS at enrollment initiation to check slot availability. Registration staff should ensure that a slot is available and secured for the patient before completing an enrollment. OSU will register all patients, including subsite patients, using IWRS.

The OPEN system will provide the site with a printable confirmation of registration and treatment information. Please print this confirmation for your records.

Patients will be registered after meeting all entry requirements, clearance by the Protocol Coordinator, and signing of the informed consent.

OSU patients will be registered by the OSU research coordinator, as per their standard practice.

Subsite patients will have eligibility verified and will be entered on study centrally at the Ohio State University by the Multi-Institution Program Coordinator. All subsites must email the Multi-Institution Program Coordinator to verify slot availabilities prior to consenting patients. The required forms, including Eligibility Criteria Checklist and Registration Form, can be found in the Supplemental Forms Document.

To register a subsite patient, the following documents must be completed by the subsite research team and faxed or securely e-mailed to the Multi-Institution Program Coordinator:

- Copy of all baseline tests required per the protocol calendar. Tests must be within the specified window.
- Signed Patient Consent Form
- Signed Patient HIPAA Authorization Form
- Consent Documentation Note
- Completed & Signed Eligibility Checklist (refer to Supplemental Forms Document)
- Registration Form (refer to Supplemental Forms Document)
- Source documents verifying every inclusion & exclusion criteria
 - Note: every inclusion and exclusion criteria must be documented in the patient's medical record

Upon receipt of registration documents, the Multi-Institution Program Coordinator will send an email confirmation of receipt. If confirmation of receipt is not received within 1 hour of submission, please call or page the Multi-Institution Program Coordinator.

Upon receipt of all required registration documents and upon verification the subsite patient meets all eligibility criteria, the Multi-Institution Program Coordinator will:

- Assign the patient a study sequence ID
- Register the patient on the study
- Fax and/or e-mail to the subsite the completed Registration Form with the assigned study sequence ID as confirmation of patient registration

Each participating institution will order study agents directly. Agents may be ordered by a participating site only after the initial IRB approval for the site has been forwarded to the Multi- Institution Program Coordinator.

Patient sequence IDs will be assigned in the following fashion:

- A-BCD
 - A = CTEP Site ID
 - BCD = sequential numbers by order of enrollment

4.4 General Guidelines

Following registration, patients should begin protocol treatment as rapidly as possible, but in no more than 7 days. Issues that would cause treatment delays should be discussed with the Principal Investigator. If a patient does not receive protocol therapy following registration, the patient's registration on the study may be canceled. The Study Coordinator should be notified of cancellations as soon as possible.

5. BIOMARKER, CORRELATIVE, AND SPECIAL STUDIES

5.1 Biomarker Plan

List of Biomarker Assays in Order of Priority

| Priority | Biomarker Name | Biomarker Assay | Biomarker Type and Purpose | M/O | Timing | Specimen | Quantity Needed | Laboratory |
|----------|---------------------------------------|---|--|-----|---|---|---|---|
| 1 | Differentiation analysis (CyTOF) | CyTOF (mass cytometry) | 
Exploratory
 
Understand mechanism of action and identify potential new biomarkers
 
CyTOF mass cytometry will be used to evaluate whether treatment with pinometostat removes the differentiation block in leukemia blasts and increases populations of mature myeloid cells; it will also be used to examine the relationship (if any) of immune effector subsets to response
 | O | Initial screening and day 8, and relapse (if applicable) | Bone marrow aspirate and peripheral blood | 
3-5 mL bone marrow aspirate
 
4-6 mL of peripheral blood
 | Laboratory of [name], PhD at The Ohio State University |
| 2 | Differentiation analysis (morphology) | Morphology differential (Wright-Giemsa) | 
Exploratory
 
Understand mechanism of action and identify potential new treatment dosing strategies
 | O | Initial screening and day 8, and relapse (if applicable). | Bone marrow aspirate and peripheral blood | 
1 mL bone marrow aspirate (as slides)
 
1 mL PB (as slides)
 | Local site CLIA lab |
| 3 | Comprehensive mutational profile | Targeted panel DNA sequencing | 
Exploratory
 
Understand pre- and post-treatment mechanisms of resistance and identify potential new biomarkers
 
This panel is much more comprehensive than the CLIA panel performed for patient care
 | O | Initial screening and relapse (if applicable) | Bone marrow aspirate | 
4 mL bone marrow aspirate
 
6 mL of peripheral blood, if blasts > 1 x 10⁹/L
 | Laboratory of [name] at The Ohio State University |

Specimen Collection Schedule

| Specimen Type | Baseline (Pre- treatment) | Day 8 of treatment | Relapse (if applicable) |
|--|--|-------------------------------|------------------------------------|
| Serum samples from peripheral blood | X | X | |
| Bone Marrow biopsy and aspirate | X | X | X |

5.2 Integral Laboratory Studies

All integral laboratory studies (metaphase karyotype, KMT2A rearrangement by FISH, and multiparameter flow cytometry) are standard of care and required to establish diagnosis and eligibility. These will be done at the site and are considered standard of care for management of AML patients.

5.2.1 MLL (KMT2A) translocation by metaphase karyotype and FISH

Background: MLL rearrangement creates a fusion protein consisting of the N terminal end of MLL and a variable number of exons from the C terminal end of a fusion partner gene. This results in the loss of MLL's SET domain (responsible for H3K4 methylation), but acquisition of additional gene-targeting activity through the fusion partner gene. Many fusion partner genes appear to activate DOT1L and thereby increase H3K79 methylation. A phase I study of the DOT1L inhibitor pinometostat has demonstrated single-agent activity in the setting of MLL rearranged relapsed/refractory acute myeloid leukemia, consistent with the pathobiology of MLL rearrangement and the drug's mechanism of action. This study is restricted to patients with MLL (*KMT2A*) rearrangements as detected by metaphase cytogenetics (karyotype) or FISH (preferred).

Method: This test which is required to establish eligibility will be performed on-site at each participating institution in a cytogenetics lab accredited by the College of American Pathologists in Clinical Cytogenetics and supervised by a cytogeneticist boarded by the American Board of Medical Genetics and Genomics in Clinical Cytogenetics.

Analysis: Details of analysis as performed at the lead institution are provided in supplementary appendices.

5.2.1.1 Collection of Specimen

4.0 mL of bone marrow aspirate should be collected in a sodium heparin tube. A single specimen tube for both metaphase cytogenetics and FISH is acceptable.

5.2.1.2 Handling of Specimen

Invert tube 3 times after collection. Specimen can be sent to the cytogenetics laboratory at room temperature, but should be processed on the same day.

5.2.1.3 Shipping of Specimen

Not applicable.

5.2.1.4 Site(s) Performing Correlative Study

This integral biomarker is required to establish study eligibility, and will be performed individually at each site.

5.2.2 Immunophenotyping by multiparameter flow cytometry

Background: Acute myeloid leukemia requires several criteria for diagnosis, including a blast percentage greater than or equal to 20%. Blasts can be sensitively distinguished by multiparameter flow cytometry, and individual blast populations (e.g., regenerative; leukemic) can be distinguished on the basis of a number of surface markers, both normal and aberrant. Evaluation of immunophenotype aids in (1) diagnosis (2) discrimination of regenerative marrow from persistent disease and (3) evaluation for minimal residual disease

Method: This test is a standard of care test that aids in the diagnosis and management of AML will be performed on-site at each participating institution in a flow cytometry lab accredited by the College of American Pathologists and/or certified according to the Clinical Laboratory Improvements Amendment (CLIA) and supervised by a pathologist boarded by the American Board of Pathology with specialization in flow cytometry.

Analysis: Detailed analysis methods as performed at the lead institution are provided in supplementary appendices.

5.2.2.1 Collection of Specimen(s)

3.0-5.0 mL of bone marrow aspirate should be collected in a sodium heparin tube.

4.0-6.0 mL of peripheral blood should be collected in a sodium heparin tube.

5.2.2.2 Handling of Specimens(s)

Invert tubes 3 times after collection. Specimen can be sent to the flow cytometry laboratory at room temperature, but should be processed on the same day.

5.2.2.3 Shipping of Specimen(s)

Not applicable.

5.2.2.4 Site(s) Performing Correlative Study

This integral biomarker is required to establish study eligibility, and will be performed individually at each site.

5.3 **Exploratory/Ancillary Correlative Studies**

5.3.1 Detection of Hematopoietic Differentiation by Mass Cytometry

CytoF (mass cytometry) will be used to evaluate whether treatment with Pinometostat removes the differentiation block in leukemia blasts and increases population proportions of mature myeloid cells; it will also be used to examine the relationship (if any) of immune effector subsets to response. These studies will be performed by [name], PhD. Briefly, bone marrow aspirates from screening and day 8 (prior to initiation of 7+3) will be fixed, permeablized, and stained with a validated custom cocktail of metal conjugated antibodies against a variety of cell surface and intracellular proteins and phospho-proteins, and run on a

Fluidigm 3rd Generation Helios Mass Cytometer in [name] laboratory. High dimensional single-cell data will be preprocessed and clustered, and visualized with SPADE and ViSNE using Cytobank platform.

5.3.1.1 Hypothesis and Rationale as it relates to future development.

We hypothesize that pinometostat will remove the differentiation block from certain subtypes of AML with a concomitant increase in the proportion of intermediate and mature myeloid cells compared to pretreatment. If this is borne out, it may suggest that certain genetically selected subsets of AML patients may be able to forego intensive induction therapy for longer or in total, or suggest that it could be justified to combine pinometostat with other complementary agents.

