2.5 Correlative Studies Background

2.5.1 Detection of Hematopoietic Differentiation by Mass Cytometry

In the EPZ-5676-012-001 study, a leukocytosis with increased numbers of polymorphonuclear cells (PMNs; neutrophils) was seen after treatment with pinometostat. In at least some cases, these PMNs were demonstrated to have MLL rearrangement by FISH, suggesting that pinometostat may act as a differentiating agent.

We plan to investigate qualitative and quantitative differences in the overall composition of hematopoietic progenitors and mature cells after 7 days of pinometostat (as a single agent) compared to pre-treatment to understand whether this agent acts through differentiation in addition to direct cytotoxicity.

Pinometostat removes active histone marks (and thereby silencers transcription) from genes involved in an aberrant stem-cell program and differentiation block including HOX family genes. Experimental silencing of these genes in other contexts has led to a differentiation phenotype. In the phase 1 study of pinometostat in relapsed or refractory AML, nine patients experienced leukocytosis manifest as increase in granulocytes and monocytes. Clinically, this is similar to the differentiation seen with treatment with all-trans retinoic acid in acute promyelocytic leukemia or IDH inhibitors in *IDH1* or *IDH2* mutant AML. An alternative, but less likely explanation, is that it could represent a drug-induced demargination of existing cells. Profiling the bone marrow aspirate for all stages of differentiation by mass cytometry can help make this distinction by detecting differences that can be too subtle to be picked up by morphology, or even conventional flow cytometry. These correlative studies will shed further light on the mechanism of action of pinometostat (or DOT1L inhibition in general) and may lead to more rational novel-novel combinations in the future.

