8.1 CTEP IND Agent

8.1.1 Pinometostat (NSC #795144)

Chemical Name or Amino Acid Sequence: (2R,3R,4S,5R)-2-(6-amino-9H-purin-9-yl)-5-((((1r,3S)-3-(2-(5-(tert-butyl)-1H-benzo[d]imidazol-2-yl)ethyl)cyclobutyl)(isopropyl amino)methyl)tetrahydrofuran-3,4-diol

Other Names: EPZ-5676, EPZ005676

Classification: DOT1L inhibitor

CAS Registry Number: 1380288-87-8

Molecular Formula: C₃₀H₄₂N₈O₃

M.W.: 562.71 g/mol

Mode of Action: Pinometostat is a selective human DOT1-like, histone H3 methyltransferase (DOT1L) inhibitor. Pinometostat exhibits concentration and time depending inhibition of global methylation of lysine 79 of histone H3 (H3K79) in cultured cells. Pinometostat induces apoptosis in cells that accumulate in the G1/G0 phase. It also inhibits the expression of the key MLL fusion target genes HOXA9 and MEIS1.

Description: A clear to yellow liquid adjusted to a pH of 5.2-6.2 with 1N sodium hydroxide or 1N hydrochloric acid as needed.

How Supplied: Pinometostat is supplied by Epizyme, Inc. and distributed by the Pharmaceutical Management Branch, CTEP/DCTD/NCI. Pinometostat injection is provided as 100 mg/10 mL (10 mg/ml) solution in type 1 borosilicate glass serum single use vials closed with butyl rubber stoppers and aluminum overseals. The other components of the vial include hydroxypropyl betadex, citric acid, anhydrous, sodium hydroxide, hydrochloric acid, and water for injection.

Preparation: Pinometostat must be diluted with 0.9% sodium chloride injection, USP prior to administration to a final concentration between 0.54 mg/ml and 5.63 mg/ml. Add the calculated dose of pinometostat to the appropriate volume of 0.9% sodium chloride in a non-DEHP PVC, polyolefin, or EVA IV infusion bag. **Note: mixing of different drug lots in the same infusion bag should be avoided.** Then gently agitate the infusion bag to ensure mixing. Up to a 90-hour dose may be prepared. An overfill volume of 10% or per institution policy can be prepared to allow for priming of the infusion set tubing. Sites should prepare the appropriate final infusion volume according to standard practice based on a constant flow rate.

Storage: Store intact vials at room temperature between 15 °C -30 °C.

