11. STUDY CALENDAR

Baseline evaluations are to be conducted within 1 week prior to start of protocol therapy. In the event that the patient's condition is deteriorating, laboratory evaluations should be repeated in order to decide if therapy should be continued.

Table 11.1: Initial treatment plan.

| | Pre-Study / Screening | Wk 1 | Wk 2 | Wk 3 | Wk 4 | Wk 5 | Off Study ^c | Long Term Follow-Up ^f |
|---|-----------------------|------|----------------|------|------|----------------|------------------------|----------------------------------|
| Pinometostat | | A | A | A | A | A | | |
| Cytarabine | | | B | | | | | |
| Daunorubicin | | | C | | | | | |
| Informed consent | X | | | | | | | |
| Demographics | X | | | | | | | |
| Medical history | X | | | | | | | |
| Concurrent meds | X | X | X | X | X | X | | |
| Physical exam | X | X | X | X | X | X | X | |
| Vital signs | X | X | X | X | X | X | X | |
| Height and Weight | X | X | X | X | X | X | X | |
| Performance status | X | | | | | | | |
| CBC w/diff, plts, PT/INR, aPTT | X | X | X | X | X | X | X | |
| Serum chemistry ^a | X | X | X | X | X | X | X | |
| EKG (as indicated) | X | | | | | | | |
| Echocardiogram/MUGA | X | | | | | | | |
| Adverse event evaluation | | X | X | X | X | X | | |
| B-HCG | X ^b | | | | | | | |
| Bone marrow aspiration and biopsy | X | | X | | X | X ^d | | |
| Bone marrow metaphase karyotype | X | | X | | X | X ^d | | |
| Bone marrow MLL (KMT2A) translocation by FISH | X | | X | | X | X ^d | | |
| Immunophenotyping (BM and PB) | X | | X | | | X ^d | | |
| Differentiation analysis | X | | X ^e | | | X ^d | | |
| Comprehensive mutational profile | X | | X ^e | | | X ^d | X | |
| Survival | | | | | | | | X ^f |

A: Pinometostat: Dose as assigned; weeks 1-5, days 1-35
B: Cytarabine: 100 mg/m² continuous IV infusion; week 2, days 8-14
C: Daunorubicin: 60 mg/m² IV; daily days 8-10 of week 2
a Albumin, alkaline phosphatase, total bilirubin, bicarbonate, BUN, calcium, chloride, creatinine, glucose, uric acid, LDH, phosphorus, potassium, total protein, SGOT [AST], SGPT [ALT], sodium.
b. Serum or urine pregnancy test (women of childbearing potential).
c. Off-study evaluation.
d. And at count recovery in week 5 or beyond
e. Day 8 of week 2, and at relapse (if applicable)

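### The differentiation hypothesis in Section 5.3.1.1 names only a rise in the mature myeloid proportion, which selective blast loss also produces; measures among non-blast cells and absolute counts should be added

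*Combined protocol and SAP*

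**What the plan says.** Section 2.5.1 plans to compare marrow composition before treatment and after seven days of single-agent pinometostat "to understand whether this agent acts through differentiation in addition to direct cytotoxicity". The rival explanation it names for the leukocytosis seen in the earlier study is that "it could represent a drug-induced demargination of existing cells".

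Section 5.3.1 says mass cytometry (CyTOF) will evaluate whether treatment "increases population proportions of mature myeloid cells". Section 5.3.1.1 states the hypothesis as removal of the differentiation block "with a concomitant increase in the proportion of intermediate and mature myeloid cells compared to pretreatment". It adds that, if this is confirmed, some genetically selected patients might be able to postpone or avoid intensive induction.

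Other planned data bear on the question:

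- Section 5.3.2: day-8 mononuclear cells are frozen, and variant allele frequency in blasts and non-blasts is examined if other correlatives already suggest differentiation.
- Section 9.3: blast counts at screening and day 8 are compared from the blood count and differential.
- Section 11, Table 11.1: the row "Bone marrow MLL (KMT2A) translocation by FISH" is marked at screening and in week 2.

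Section 5.3.1.2 calls the CyTOF data exploratory, and Section 9.4.2 plans descriptive statistics for all correlatives. No section uses absolute mature-cell counts or the week-2 FISH result to decide whether blasts have matured.

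**The concern.** The denominator of the proportion contains the blasts. If blasts disappear, every other population takes a larger share, whether or not any blast has matured. Blast death is an effect the protocol itself expects: Section 8.1.1 says "Pinometostat induces apoptosis in cells that accumulate in the G1/G0 phase". So the one observable named in the hypothesis can be satisfied by the explanation it is meant to be distinguished from.

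What is at stake is the mechanistic reading of the biomarker ranked first in Section 5.1. Section 5.3.1.1 ties a positive result to ideas about future treatment strategy and combinations, so a mistaken reading could carry into later studies.

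**Working it through.** The documents give no figure for the CyTOF readout, so there is none to reproduce. The marrow compositions and kill fractions below are assumptions. The documents supply only a lower limit for blasts: Section 5.2.2 says diagnosis requires "a blast percentage greater than or equal to 20" percent.

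**Notation.** Per 100 baseline cells: b blasts, m mature myeloid, o other. A fraction k of blasts is killed, or a fraction d matures one for one.

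**Step 1: the proportion under each mechanism.**

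- Kill only: m / [b(1−k) + m + o]
- Maturation only: (m + b·d) / (b + m + o)

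For 70/10/20 and k = 0.5: 10 / (35 + 10 + 20) = 10/65 = 15.4%. The matching maturation is d = (15.4 − 10)/70 = 7.7%.

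| Marrow b/m/o | Blasts killed | Mature share | Same share from maturation of |
|---|---|---|---|
| 70/10/20 | 25% | 10/82.5 = 12.1% | 3.0% of blasts |
| 70/10/20 | 50% | 10/65 = 15.4% | 7.7% |
| 70/10/20 | 80% | 10/44 = 22.7% | 18.2% |
| 50/15/35 | 50% | 15/75 = 20.0% | 10% |
| 85/5/10 | 50% | 5/57.5 = 8.7% | 4.3% |
| 20/40/40 | 50% | 40/90 = 44.4% | 22.2% |

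**Step 2: when the share rises.** If mature and other cells also fall, both by a fraction j, the share is m(1−j) / [b(1−k) + (m+o)(1−j)]. For 70/15/15 with half the blasts lost, j = 0, 25%, 50% and 75% give 23.1%, 19.6%, 15.0% and 8.8%, from a baseline of 15%. The share rises only if k exceeds j.

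**Step 3: share among non-blast cells, m/(m+o).** Blasts do not enter it, so neither k nor a common j changes it.

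- 70/10/20: 10/30 = 33.3% before and after kill; with 7.7% maturation, 15.4/35.4 = 43.5%.
- 50/15/35: 15/50 = 30% before and after kill; with 10% maturation, 20/55 = 36.4%.
- 20/40/40: 40/80 = 50% before and after kill; with 22.2% maturation, 44.4/84.4 = 52.6%, so the contrast is small when blasts are few.
- Limit: if only the other cells fall, by 25%, the 70/10/20 marrow gives 10/25 = 40% without maturation.

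**Step 4: absolute mature cells.** In 70/10/20 they stay at 10 under kill and rise to 15.4 under 7.7% maturation.

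**Step 5: KMT2A FISH in marrow.** Assume all blasts are FISH-positive.

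- Simple difference, FISH% − blast%: if the 10 mature cells are already clonal, it is 80 − 70 = 10 points at baseline. After 50% kill it is 45/65 − 35/65 = 69.2 − 53.8 = 15.4 points. Kill alone moves it.
- Rearranged share of non-blasts, (FISH% − blast%) / (100 − blast%): 10/30 = 33.3% at baseline and 15.4/46.2 = 33.3% after kill, so unchanged. With 7.7% maturation it becomes 15.4/35.4 = 43.5%. With no clonal non-blasts at baseline it goes from 0 to 5.4/35.4 = 15.2%.
- Noise: at 64.6% blasts, an assumed 5-point FISH error shifts this share by 5/35.4 = 14 points, about the size of that 15.2-point signal.

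**The case against.** The strongest reply is that the proportion is not the whole readout. Section 2.5.1 says: "We plan to investigate qualitative and quantitative differences in the overall composition of hematopoietic progenitors and mature cells". Section 5.3.1 describes single-cell profiling of surface, intracellular and phospho-proteins, which may show maturation patterns directly. Section 5.1 adds morphology, Section 9.3 adds blast counts, and Section 5.3.2 adds a clonal check that a false signal would itself trigger. Gating and normalisation may be set out in the biomarker submission (Section 5.3.1.5) or the laboratory attachments (Appendix D), which are not part of these documents. The results are exploratory.

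Much of this stands. A reader might infer that the mature share rises whenever blasts die, that the whole plan is unable to tell the mechanisms apart, or that any active drug would be labelled a differentiating agent. The documents support none of these. Step 2 shows the share can stay flat or fall, other relevant data are collected, and there is no threshold or decision rule that would apply such a label.

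The safeguards are nevertheless partial. The sequencing step waits for a differentiation signal that may be the confounded one. It needs a trackable mutation, and Section 2.5.2 describes few in this disease. It uses mononuclear cells, although the cells that raised the question in Section 2.5.1 were polymorphonuclear. Section 5.1 lists the panel at screening and relapse only, whereas Section 5.3.2 and Table 11.1 include day 8; these need reconciling. Morphology differentials are also proportions, and no qualitative pattern is defined as differentiation.

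It is also fair to object that remedies have weaknesses of their own. Blood counts are open to demargination and to hydroxyurea, which Section 3.1.3 permits before and during treatment. The simple FISH-minus-blast difference fails as shown in Step 5.

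**Conclusion.** The concern holds in a limited form. Taken alone, the proportion named in Section 5.3.1.1 cannot separate differentiation from selective cytotoxicity, the question posed in Section 2.5.1. Under the assumed compositions, a 50% blast kill with no maturation is indistinguishable from maturation of 4.3% to 22.2% of blasts (7.7% in the 70/10/20 marrow).

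This rests on assumed marrow compositions, an assumed extent of kill by day 8, and blasts falling by a larger fraction than other cells. The documents do not say how much blast loss to expect after seven days. The effect is confined to the interpretation of an exploratory correlative. It is worth correcting because the repair uses samples and tests already scheduled.

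**What to change.** In Section 5.3.1, keep the proportions as descriptive results and add, at screening and at day 8 before 7+3:

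1. Intermediate and mature myeloid cells as a share of non-blast cells by CyTOF.
2. Change in absolute mature myeloid counts in blood, from the blood count and differential, reported with hydroxyurea use and read with demargination in mind.
3. As supportive evidence, the rearranged share of non-blast marrow cells, (FISH% − blast%) / (100 − blast%), from the screening and day-8/week-2 marrow, in place of any simple difference.

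State that differentiation is inferred only when these measures rise, with the third in a supporting role, and not from the raw proportion alone.

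The cost is a wording change and a small amount of analysis; no new sample or visit is needed. The downsides should be stated: FISH and blast percentages come from local laboratories and are noisy; the third measure assumes every blast is FISH-positive; the first can move if non-blast populations fall unequally; and blood counts can be confounded by hydroxyurea or demargination.
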